4 SELECTION AND ENROLLMENT OF PARTICIPANTS

4.1 Inclusion Criteria

Participants will be eligible if they meet the following criteria:

- Age 18 years or older
- Live with PLWD or within 5 miles
- Provide at least 8 hours of care per week
- Self-identify as Hispanic/Latino
- Caregiver self-report of PLWD having ≥ 3 BPSD occurring ≥ 3 in past week

4.2 Exclusion Criteria

Participants will be excluded if:

- PLWD lives in assisted living or skilled nursing facilities

4.3 Study Enrollment Procedures

We will identify potential study participants using a variety of strategies. First, we will contact Latino caregivers of PLWD who receive care at UW Medicine. These individuals participated in a previous study led by [name] and agreed to be contacted again for participation in future studies. Second, we will distribute recruitment flyers in federally qualified health centers and across primary care clinics that are part of the WWAMI (Washington, Wyoming, Alaska, Montana and Idaho) region Practice and Research Network. Next, we will advertise the study in Spanish language media (e.g., radio

stations and newspapers). Finally, we will recruit via the Alzheimer’s Prevention Registry.

For caregivers who are interested in study participation, the study staff members, [name] and [name], will schedule a phone call to answer any questions they may have and screen for eligibility. We will email or mail the consent form to caregivers who are eligible. After mailing these materials, study staff will contact caregivers by phone to review the consent form and answer any questions. Caregivers will sign the consent form electronically or by paper and mail it to staff members. After receiving the signed consent form, caregivers will receive an email or text message asking them to complete the online baseline survey. Participants who do not sign the consent form will not be allowed to participate in the study. We will use a screening log to document reasons for ineligibility and for non-participation of eligible candidates.

5 STUDY INTERVENTIONS

5.1 Interventions, Administration, and Duration

For 6-8 weeks, caregivers will complete the 7 online training modules asynchronously. As described in Table 2, the content of the modules includes an overview of dementia, realistic expectations, effective communication, using the ABC approach to problem-solve BPSD, and planning pleasant events. Each module takes about 15 minutes to complete. We will instruct caregivers to complete one module per week. The modules use text, pictures, and illustrations with a voiceover presentation. The modules also include an adapted workbook with for participants to complete. ***While the STAR-VTF intervention incorporates a coaching component, the present study will only pilot test the adapted online training modules.*** The full STAR-VTF intervention – adapted modules coupled with coaching – will be tested in a future study with Latino caregivers.

We believe there is minimal risk associated with participating in the study. The intervention is an education and training program to give caregivers more tools and better knowledge for minimizing and responding to BPSD. The primary risk with the intervention is discomfort with the intervention content. The intervention’s recommendations based on the best available clinical evidence and has already been extensively tested in prior research. Core elements of the intervention have been proven in previous research to significantly improve average clinical outcomes. Nevertheless, treatment recommendations that improve care on average may have adverse consequences for any individual patient. Participants will be fully informed of the risks and their right to decline or withdraw from the study or specific activities.

5.2 Handling of Study Interventions

From home, caregivers will access the asynchronous, self-directed modules via a website hosted on the Kaiser Permanente School of Allied Health Sciences learning management system. Caregivers will log in to the website from their preferred web browser using an email address and user-generated password.

5.3 Concomitant Interventions

The intervention is an adjunct to usual care. No services that are usually available to PLWD or their family caregivers will be withheld.

5.4 Adherence Assessment

Caregiver adherence data will be captured automatically via the Kaiser Permanente School of Allied Health Sciences learning management system. There are built-in metrics that track how users interact with the website, which we will utilize to determine caregiver completion rates for each module. We will use descriptive statistics to characterize caregiver adherence to completing the modules.

6 STUDY PROCEDURES

6.1 Schedule of Evaluations

Assessment	Screening Assessment (Week 0)	Baseline Assessment (Week 0)	Module Assessments (Weeks 1-6)	Final Assessment (Weeks 7-8)
Inclusion/Exclusion Criteria	X			
Informed Consent Form	X			
Enrollment	X			
Sociodemographic characteristics		X		
Revised Memory and Problem Behavior Checklist		X		X
Preparedness for Caregiving Scale		X		X
Perceived Usability of Modules			X	
Qualitative Assessment of Intervention Acceptance				X

6.2 Description of Evaluations

6.2.1 Screening Assessment

For caregivers who are interested in study participation, the study staff members will schedule a phone call to answer any questions they may have and screen for eligibility. Study staff will use a structured screening survey to ask potential participants their age, whether they live with PLWD or within 5 miles, the number of hours of care they provide each week, their race/ethnicity, and whether PLWD lives in assisted living or skilled nursing facilities.

We will email an e-consent form to caregivers who are eligible. After emailing these materials, study staff will contact caregivers by phone again to review the e-consent form and answer any questions. Caregivers will be instructed to sign the e-consent form. Enrollment will begin when the study staff members receive the e-consent forms signed by caregivers.

6.2.2 Baseline Assessment

After receiving the signed e-consent form, caregivers will receive an email or text message asking them to complete the REDCap baseline survey that contains:

- Sociodemographic questionnaire
- Revised Memory and Problem Behavior Checklist
- Preparedness for Caregiving Scale

6.2.3 Module Assessment

At the end of each online training module, there is a short survey that caregivers are asked to complete. The survey contains:

- System Usability Scale

6.2.4 Final Assessment

After 6-8 weeks post-enrollment, caregivers will receive an email or text message asking them to complete the REDCap baseline survey that contains:

- Revised Memory and Problem Behavior Checklist
- Preparedness for Caregiving Scale

In addition, study staff members will schedule an exit interview with participants. The interview will happen virtually (phone or videoconferencing) and will be under 1 hour. We will ask participants semi-structured questions to gauge their acceptance of the online learning modules and their experience completing the REDCap survey.

7 SAFETY ASSESSMENTS

7.1 Potential Risks and Benefits for Participation

Potential Risks: We believe there is minimal risk associated with participating in the study. The primary risks to participation are:

- Breach of confidentiality
- Discomfort in answering survey or interview questions
- Discomfort with the intervention content

Potential Benefits: We anticipate that this research will yield important new information regarding the delivery of culturally competent support to Latino caregivers of PLWD. The results of the study will help to improve future care for Latino caregivers.

7.2 Adverse Event (AE) and Serious Adverse Event (SAE) Collection and Reporting

7.2.1 AE/SAE Definitions

The study will adhere to the definitions for AEs and SAEs stipulated in the [NIA Adverse Event and Serious Adverse Event Guidelines](#) as outlined below.

AE Definition: AE is any untoward or unfavorable medical occurrence in a human study participant, including increased stressed, inability to cope, or other emotional discomfort, temporally associated with the participants' involvement in the research, whether or not considered related to participation in the research.

AEs for this study include:

This study is designed to pilot test a behavioral intervention with caregivers. As such, we believe it will pose minimal risk to participants because the probability and magnitude of harm or discomfort anticipated are not greater in and of themselves than those ordinarily encountered in daily life or during the performance of routine physical or psychological examinations or tests. The risks of participating in this study may include feeling discomfort discussing personal matters during the intervention, survey, or exit interview, as well as frustration as caregivers attempt to implement the suggestions of the STAR-VTF online learning modules.

SAE Definition: SAEs consist of any adverse event that results in death; is life threatening or places the participant at immediate risk of death from the event as it occurred; requires or prolongs hospitalization; causes persistent or significant disability or incapacity; results in congenital anomalies or birth defects; is another condition which investigators judge to represent significant hazards

SAEs for this study include:

Research activities may identify immediate risk of harm or other urgent need. While we would not conclude that any such emergencies are consequences of study participation or

intervention content, there is still a clear obligation to report and respond appropriately to these urgent needs.

7.2.2 Classification of Severity and Study Relatedness

All data and safety monitoring reporting will classify SAEs and AEs as to their severity, expectedness, and potential relatedness to the study intervention as per the definitions below:

Severity

- **Mild:** Awareness of signs or symptoms, but easily tolerated and are of minor irritant type causing no loss of time from normal activities. Symptoms do not require therapy or a medical evaluation; signs and symptoms are transient.
- **Moderate:** Events introduce a low level of inconvenience or concern to the participant and may interfere with daily activities, but are usually improved by simple therapeutic measures; moderate experiences may cause some interference with functioning
- **Severe:** Events interrupt the participant's normal daily activities and generally require systemic drug therapy or other treatment; they are usually incapacitating

Expectedness

- **Unexpected** - nature or severity of the event is not consistent with information about the condition under study or intervention in the protocol, consent form, product brochure, or investigator brochure.
- **Expected** - event is known to be associated with the intervention or condition under study.

Unexpected events will be subject to expedited reporting requirements as described in the [NIA Guidance on Clinical Trials](#) and in Section 1.2.3, below.

Relatedness

- **Definitely Related:** The adverse event is clearly related to the investigational agent/procedure – i.e. an event that follows a reasonable temporal sequence from administration of the study intervention, follows a known or expected response pattern to the suspected intervention, that is confirmed by improvement on stopping and reappearance of the event on repeated exposure and that could not be reasonably explained by the known characteristics of the subject's clinical state.
- **Possibly Related:** An adverse event that follows a reasonable temporal sequence from administration of the study intervention follows a known or expected response pattern to the suspected intervention, but that could readily have been produced by a number of other factors.
- **Not Related:** The adverse event is clearly not related to the investigational agent/procedure - i.e. another cause of the event is most plausible; and/or a clinically plausible temporal sequence is inconsistent with the onset of the event

and the study intervention and/or a causal relationship is considered biologically implausible.

7.2.3 AE/SAE Reporting

The study will adhere to the reporting requirements for AEs and SAEs stipulated in the [NIA Adverse Event and Serious Adverse Event Guidelines](#) as outlined below.

Process for identifying AEs and SAEs: The study staff members, [name] and [name], will be in contact with participants while carrying out research activities and will be able to identify any AEs and SAEs that occur. When an adverse event is identified, [name] and study staff will follow [NIA's AE/SAE process flow](#). They will meet on a weekly basis throughout the project period and will review study progress and adverse events. NIA's [template for AEs](#) and [template for SAEs](#) will be used to collect information about adverse events.

Adverse event reporting schedule:

- All **adverse events that are both serious (SAE) and unexpected** (i.e., have not been previously reported for the study's intervention) will be reported to the IMPACT Collaboratory Regulatory and Data Team Leader ([name] PhD), Advarra IRB, NIA IMPACT Collaboratory PO ([name]), and the IMPACT Collaboratory DSMB Chair (or the project's Safety Officer) within 48 hours of the study's knowledge of SAE.
- The summary of all other SAEs will be reported to IMPACT Collaboratory Regulatory and Data Team Leader ([name] PhD), Advarra IRB, NIA IMPACT Collaboratory PO ([name]), and the IMPACT Collaboratory DSMB Chair (or the project's Safety Officer) quarterly, unless otherwise requested by the DSMB Chair or a Safety Officer.
- All deaths will be reported to IMPACT Collaboratory Regulatory and Data Team Leader ([name] PhD), Advarra IRB, NIA IMPACT Collaboratory PO ([name]), and the IMPACT Collaboratory DSMB Chair (or the project's Safety Officer) and to the DSMB Chair (or project's Safety Officer) within 24 hours of study's knowledge of death.
- AEs will be reported per IRB policies and also to IMPACT Collaboratory Regulatory and Data Team Leader ([name] PhD), Advarra IRB, NIA IMPACT Collaboratory PO ([name]), and the IMPACT Collaboratory DSMB Chair (or the project's Safety Officer) and to the DSMB Chair (or project's Safety Officer) at minimum every 6 months, or at a frequency requested by NIA and/or by the DSMB.

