psychology, social work, or a related field) visit caregivers at home to deliver the training.²² The condensed 6-week program involves 4 in-home sessions and 2 telephone sessions.^{23,24} A randomized controlled trial was conducted to compare STAR-C to routine medical care in English-speaking, predominantly White participants.²³ The study population included only 1 Latino caregiver (randomized to control arm). At 6 months, caregivers randomized to the intervention arm had significantly lower depression, subjective burden, and caregiver reaction scores.

To ease translation, STAR-VTF was developed and is now being tested in a pragmatic trial at Kaiser Permanente Washington (KPWA).^{25,26} STAR-VTF delivers the same content as STAR-C but in an entirely virtual environment.²⁶ For 6-8 weeks, caregivers complete 6 online training modules asynchronously and have 6 30-minute weekly telephone check-ins with a coach (social worker or mental health counselor). The 6 modules cover the same content as STAR-C (Table 1). The modules are hosted on the Kaiser Permanente School of Allied Health Sciences learning management system. Currently, only caregivers participating in the ongoing pragmatic trial at KPWA have access to this website. Our preliminary data identified potential areas of misfit between STAR-VTF and Latino caregivers. The modules: do not sufficiently address dementia literacy, use language/semantics that could be insensitive, and do not reflect Latino cultural values that could influence family structures and views of caregiving.

Table 1. STAR-VTF Modules	
1	Introduction to behavioral treatment of dementia, realistic expectations, & effective communication
2	ABC approach to problem-solving, including rationale & development of an ABC plan
3	Review of ABC plan and revise if needed
4	Increasing pleasant events & managing negative thinking
5	Review of ABC plan, pleasant events schedule, & revise if needed
6	Coping with caregiving and maintaining gains

Table 2. Adapted STAR-VTF Modules	
1	Understanding and overview of dementia
2	Introduction to behavioral treatment of dementia, realistic expectations, & effective communication
3	ABC approach to problem-solving, including rationale & development of an ABC plan
4	Review of ABC plan and revise if needed
5	Increasing pleasant events & managing negative thinking
6	Review of ABC plan, pleasant events schedule, & revise if needed
7	Coping with caregiving and maintaining gains

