Caregivers will complete a baseline survey using a REDCap link that will be delivered to caregivers via email or text message. The survey will include sociodemographic characteristics and the outcome measures (i.e., Revised Memory and Problem Behavior Checklist and Preparedness for Caregiving Scale). We will collect outcome measures from caregivers again 6-8 weeks post-enrollment using the same data collection method. Sociodemographic characteristics will include: caregiver age, occupational status, whether caregiver works outside of the home, number of people living in caregiver’s home, educational attainment, English fluency, preferred language, languages spoken at home, race, gender, annual household income, device ownership, Internet access at home, health insurance status of caregiver and PLWD, relationship to PLWD, age of PLWD, gender of PLWD, number of years in caregiving role, whether caregiver lives in same household as PLWD, and hours per week providing care.

After completing the baseline survey, caregivers will begin participation in the intervention. ***The intervention tested in this study will only involve the self-directed training component of the STAR-VTF intervention.*** We will provide caregivers with the video modules via text message or email. We will also mail each participant a copy of the adapted version of the STAR-VTF workbook in their preferred language. There are handouts and resources to along with each lesson. Caregivers will be instructed to complete 1 module per week for 7 weeks (Table 2).

After 6-8 weeks, we will schedule an exit interview with caregivers. The interview will happen virtually (phone or videoconferencing) and will be under 1 hour. We will ask participants semi-structured questions to understand their experience with the online training modules and with completing the survey via REDCap.

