16 SUPPLEMENTS/APPENDICES

I. Outcome Measures

Revised Memory and Behavior Checklist

Instructions: The following is a list of problems patients sometimes have. Please indicate if any of these problems have occurred during the past week. If so, how much has this bothered or upset you when it happened Use the following scale for your reaction. Please read the description of the ratings carefully.

Has it occurred in the past week:

0 = No
1 = Yes

Reaction Ratings:

0 = not at all
1 = a little
2 = moderately
3 = very much
4 = extremely

Please answer all the questions for both frequency and reaction.

(RC11)

Problem	Has it occurred? (in past week)		Reaction (how much it bothered you)
1. Asking the same question over and over	NO	YES	
2. Trouble remembering recent events (i.e. items in newspaper or TV)	NO	YES	
3. Trouble remembering significant past events	NO	YES	
4. Losing or misplacing things	NO	YES	
5. Forgetting what day it is	NO	YES	
6. Starting, but not finishing, things	NO	YES	
7. Difficulty concentrating on a task	NO	YES	
8. Destroying property	NO	YES	
9. Doing things that embarrass you	NO	YES	
10. Waking you or other family members up at night	NO	YES	
11. Talking loudly and rapidly	NO	YES	
12. Appears anxious or worried	NO	YES	
13. Engaging in behavior that is potentially dangerous to self or others	NO	YES	
14. Threats to hurt oneself	NO	YES	
15. Threats to hurt others	NO	YES	
16. Aggressive to others verbally	NO	YES	
17. Appears sad or depressed	NO	YES	
18. Expressing feelings of hopelessness or sadness about the future	NO	YES	
19. Crying and tearfulness	NO	YES	
20. Commenting about death of self or others	NO	YES	
21. Talking about feeling lonely	NO	YES	
22. Comments about feeling worthless or being a burden to others	NO	YES	
23. Comments about feeling like a failure, or about not having any worthwhile accomplishments in life	NO	YES	
24. Arguing, irritability, and/or complaining	NO	YES	

The Preparedness for Caregiving Scale

YOUR PREPARATION FOR CAREGIVING

We know that people may feel well prepared for some aspects of giving care to another person, and not as well prepared for other aspects. We would like to know how well prepared you think you are to do each of the following, even if you are not doing that type of care now.

	Not at all prepared	Not too well prepared	Somewhat well prepared	Pretty well prepared	Very well prepared
1. How well prepared do you think you are to take care of your family member's physical needs?	0	1	2	3	4

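### Section 7.2.3 relies on staff contact to identify every adverse event, but no live contact is scheduled during the module weeks and no instrument shown asks about events

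*Combined protocol and SAP*

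**What the plan says.** **How events are to be found.** Section 7.2.3 says that the study staff "will be in contact with participants while carrying out research activities and will be able to identify any AEs and SAEs that occur". The process flow and reporting templates it links to are brought in once an event has been identified. The investigator and staff meet weekly and review adverse events.

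**What counts as an event.** Section 7.2.1 defines AEs broadly. Emotional events such as greater stress or not coping are included, and relatedness to the study is not required. It expects some frustration when caregivers try out what the modules suggest. It also says research activities may bring urgent needs to light, and that "there is still a clear obligation to report and respond appropriately to these urgent needs".

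**How the intervention is delivered.** Section 3 says "The intervention tested in this study will only involve the self-directed training component of the STAR-VTF intervention". Section 5.1 confirms that "the present study will only pilot test the adapted online training modules". By contrast, Section 2.1 describes caregivers in the parent programme, who "have 6 30-minute weekly telephone check-ins with a coach".

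**What is scheduled.** In Section 6.1 the only row marked for the module weeks is perceived usability. The final assessment has the two outcome scales and a row for "Qualitative Assessment of Intervention Acceptance". There is no row for adverse events.

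**The concern.** The identification process depends on contact that the design has largely removed. Stress, frustration and trouble coping would arise at home during the module weeks and may leave no trace in study records unless someone asks. The weekly team meeting can only review events that have already reached the team.

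Two things are at stake:

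- **Timeliness.** The 24-hour clock for deaths and the 48-hour clock for serious unexpected events in Section 7.2.3 both start when the study learns of the event. An event first heard of at the exit interview could be reported weeks after it happened without breaching the rule.
- **Interpretability.** AE summaries are due at least every 6 months. A summary with no events would be uninformative, because the absence of events and the absence of questions look the same.

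**Working it through.** The plan states no figure on this point, so there is none to reproduce. The check sets every scheduled contact and instrument beside the claim in Section 7.2.3.

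| Contact or instrument | When | Live? | Asks about events? | Source |
|---|---|---|---|---|
| Screening call | Before modules | Yes | No, eligibility only | 4.3, 6.2.1 |
| Consent call | Before modules | Yes | No | 4.3, 6.2.1 |
| Baseline survey | Week 0 | No, link | No | 6.2.2, 10.1 |
| Modules and adherence tracking | 6-8 weeks | No, automatic | No | 5.1, 5.4 |
| System Usability Scale | End of each module | No, self-completed | No; free text is about the website | 6.2.3, 9.4.2, 10.1, Appendix I |
| Final survey | 6-8 weeks | No, link | No; upset is rated only for behaviours of the person with dementia in the past week | 6.2.4, Appendix I |
| Exit interview | After 6-8 weeks | Yes | Not among the stated topics; guide still to be written | 3, 6.2.4, 9.4.2 |
| Weekly log and team meeting | Weekly | No participant present | Log covers survey prompts and interview scheduling | 10.3.3, 7.2.3 |

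1. **Live contacts.** Three are scheduled. Two come before the modules and one after, so none falls in the module weeks.
2. **What was removed.** The parent programme's coaching gave 6 × 30 = 180 minutes of live contact per caregiver. Here it is zero. The documents do not say that those calls collected AEs, only that they were a regular opportunity to hear of them.
3. **Event questions.** None appears in the schedule, in the instruments in Appendix I, or in the data collection forms of Section 10.1.
4. **Against the definition.** The closest item is the checklist's reaction rating. It covers one week of a 6-8 week period and concerns reactions to another person's behaviour, so it does not stand in for an AE question.

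**Illustration only.** The capture rates c below are assumptions; the documents give none. With n caregivers and no events recorded, the one-sided 95% upper bound p on per-caregiver risk solves (1 − c·p)^n = 0.05, so p = (1 − 0.05^(1/n)) / c.

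- n = 20, c = 1: 1 − 0.05^(1/20) = 13.9%
- n = 20, c = 0.75: 0.1391 / 0.75 = 18.5%
- n = 20, c = 0.5: 0.1391 / 0.5 = 27.8%
- n = 20, c = 0.25: 0.1391 / 0.25 = 55.6%
- n = 5, c = 1: 1 − 0.05^(1/5) = 45%. Five is the recruitment floor in Section 9.3.

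These show only the direction: incomplete capture weakens a zero count that the sample size already makes weak.

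**The case against.** **Other routes to events exist.** A reader might infer that events in the module weeks will all be missed. The documents do not support that. The exit interview is live and, in Section 3, explores caregivers' experience with the modules, which could well bring out frustration or discomfort. Section 8 records reasons for discontinuation and allows follow-up with permission. Caregivers may also volunteer events. This objection stands: the supportable claim is that events can be missed or learned of late. These routes are still incidental and do not amount to identifying any event that occurs.

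**Some material cannot be seen.** The interview guide is not yet written, the consent form is not in the review copy, and the linked templates are not reproduced. So the statement that nothing asks about events is limited to the visible text. Reporting instructions in a consent form would be spontaneous reporting and would not replace a scheduled question.

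**Checklist items 13-15.** A reader might take a yes to "Engaging in behavior that is potentially dangerous to self or others", or to the two items on threats, as an uncaptured AE. It is not one. The items describe the person with dementia, while the enrolled participant is the caregiver. Eligibility requires several behavioural symptoms, so some positive answers are to be expected. Only the urgent-needs sentence in Section 7.2.1 makes these items relevant, and that is a separate matter.

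**No safety inference is planned.** A reader might infer that the plan intends to cite zero events as evidence of safety. It makes no such claim: no hypotheses are tested, there is no safety outcome and analyses are descriptive. That is why the bounds above are illustration and not part of the finding. It does not remove the gap between what Section 7.2.3 states and what the schedule provides.

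**Conclusion.** The point holds in a limited form. Followed as written, the plan does not give staff the ability that Section 7.2.3 claims for them. Its extent is 6-8 weeks with no scheduled live contact, and no scheduled event question at any time, including the final assessment. The consequence is possible under-ascertainment and late ascertainment of AEs. It is not certain loss, and its size cannot be estimated from the documents.

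The conclusion rests on the visible text and on the assumption that the unwritten interview guide would follow the topics stated in Sections 3 and 6.2.4. It does not depend on any assumed capture rate. In a minimal-risk educational pilot this is a change that should be made because it is cheap; it does not threaten the study's objectives.

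The route for checklist items 13-15 is a separate, smaller point. The final and baseline surveys arrive by link, and no described step brings a positive answer to staff, so the obligation in Section 7.2.1 has no mechanism behind it.

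**What to change.** 1. Add an adverse event row to Section 6.1.
2. Add one short fixed question matching the Section 7.2.1 definition to the final REDCap survey and to the exit interview guide.
3. Preferably add the same question to the end-of-module survey, which is the only instrument in the module weeks. First reconcile where that survey sits: Section 9.4.2 embeds it in the modules, while Section 10.1 sends it as a REDCap link. The answer decides whether and when staff see the responses.
4. Reword Section 7.2.3 to describe these questions as the identification process, alongside volunteered reports.
5. Separately, set a REDCap notification to study staff when checklist item 13, 14 or 15 is marked yes. How staff respond is for the investigators to specify.

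**Cost.** One question, one notification setting and IRB review of the wording. The real burden is follow-through, because the definition counts events regardless of relatedness and each positive answer must be classified and reported. With 20 caregivers, the final survey and interview add up to 20 × 2 = 40 queries. Adding the seven module surveys makes it 20 × (7 + 2) = 180. If that is too much, steps 1, 2 and 4 are the minimum, accepting that events in the module weeks would then be learned of at the end and from recall.
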